### **8.3 Analysis of the exploratory endpoints**

**Genome-wide mRNA expression data** will also be collected with comparisons made both within and between treatment groups. This analysis will look for expression based indications of molecular pathway alterations upon exposure to LDE225 and will do so in an unbiased way. For each array, data will be processed for statistical analysis using packages from R/Bioconductor with a mixed-effects model used to fit for each gene and to estimate expression differences between groups and an empirical Bayesian approach used to moderate log2 fold change standard errors. Functional themes will be obtained from Gene Ontology, Kyoto Encyclopedia of Genes and Genomes, the Human Protein Reference Databases and Molecular Signature Databases and used to perform enrichment analysis using Wilcoxon tests. Multiple testing corrections will be performed using the Benjamini-Hochberg method.

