### 3      **Investigational Plan**

#### 3.1      **Overview and study design**

This pharmacodynamic/phase 0 trial is designed as a randomized two-arm (LDE225 vs. observation groups) open-label prospective clinical trial in men with localized high-risk prostate cancer undergoing radical prostatectomy.

Activation of the Hedgehog pathway is most reliably indicated by increased expression of the *GLI1* transcription factor. Quantitative RT-PCR (qRT-PCR) provides the most reliable means to assess changes in *GLI1* expression upon exposure to drug and will be used as our primary readout. Our intent will be to examine the fold change in *GLI1* expression in each man following exposure to drug (comparing pre-operative needle biopsy tissue to surgical tissue obtained from the same man's prostatectomy specimen). Because the effects of surgery and fluctuations in hedgehog signaling in the prostate are unknown, *GLI1* expression will also be compared between biopsies and prostatectomy specimens for men without drug exposure. As treatment with LDE225 may alter the gene expression of other Hedgehog pathway members and affect separate signaling pathways, as an exploratory goal, we will perform genome-wide expression analysis using the GeneChip Human Exon 1.0ST Array (Affymetrix) and will confirm fluctuations in selected genes of interest.

High-risk patients will be identified based on their core-needle biopsy features, PSA levels, and clinical stage. Eligible men (NCCN high-risk (Gleason sum  $\geq 8$ , or PSA  $>20$  or clinical stage  $\geq T3$  with no evidence of metastatic disease) will undergo a repeat prostate biopsy at Johns Hopkins with multiple (up to 12) cores taken from the area of their primary lesion. This tissue will be frozen fresh and used for analysis of *Gli1* mRNA expression and array analysis as well as mounted for pathological analysis and IHC analysis of proliferation (Ki-67) and apoptosis (cleaved caspase-3) markers.

[figure not shown]

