### **6.2.4 Biomarkers**

For analysis of *Gli1* expression, RNA will be purified using the RNeasy Minikit (Qiagen) and then cDNA will be synthesized according to standard procedures. Quantitative PCR will then be performed using the Taqman system with primers for *Gli1* and the reference gene *HPRT1*. Applied Biosystems software will be used to calculate threshold cycle values (and thus relative expression levels). Normalized changes in *Gli1* expression between each patient pre- and post-operatively and between each group (observation versus treatment arm) will be made with 2-sided pairwise comparisons considering  $P < 0.05$  to be statistically significant.

Genome-wide mRNA expression data will also be collected with comparisons made both within and between treatment groups. This analysis will look for expression based indications of molecular pathway alterations upon exposure to LDE225 and will do so in an unbiased

way. For each array, data will be processed for statistical analysis using packages from R/Bioconductor with a mixed-effects model used to fit for each gene and to estimate expression differences between groups and an empirical Bayesian approach used to moderate log2 fold change standard errors. Functional themes will be obtained from Gene Ontology, Kyoto Encyclopedia of Genes and Genomes, the Human Protein Reference Databases and Molecular Signature Databases and used to perform enrichment analysis using Wilcoxon tests. Multiple testing corrections will be performed using the Benjamini-Hochberg method.

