### **8.1      Sample size considerations, and analysis of the primary endpoint**

The primary endpoint is a  $\geq 50\%$  reduction in *Gli1* mRNA (or protein) expression following treatment with LDE225. This study will compare prostatectomy *Gli1* expression levels to presurgical biopsy *Gli1* expression levels in the same patients (*i.e.* intra-patient changes). In the control group (observation), we expect  $<10\%$  of patients to show a  $\geq 50\%$  *Gli1* downregulation (null hypothesis), while in the LDE225 group we would hypothesize that  $>50\%$  of patients would demonstrate a  $\geq 70\%$  *Gli1* downregulation (alternative hypothesis). Using a 2-sided alpha ( $\alpha$ ) of 0.10 and a beta ( $\beta$ ) of 0.20 (power = 80%), a sample size of **11 men/arm** (total = **22men**) would be required to observe a difference in the primary endpoint from  $<10\%$  (in the control arm) to  $\geq 70\%$  (in the LDE225 arm).

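### The planned Wilcoxon gene-set enrichment makes no allowance for correlation between genes, so on its ordinary reading the pathway P values are too small and Benjamini-Hochberg does not control false discoveries

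*Combined protocol and SAP*

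**What the plan says.** Sections 6.2.4 and 8.3 describe the same sequence for the array data:

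- Each gene is analysed separately, "with a mixed-effects model used to fit for each gene", with "an empirical Bayesian approach used to moderate log2 fold change standard errors".
- Gene sets come from public annotation sources: "Functional themes will be obtained from Gene Ontology, Kyoto Encyclopedia of Genes and Genomes", and two further databases.
- These sets are "used to perform enrichment analysis using Wilcoxon tests".
- "Multiple testing corrections will be performed using the Benjamini-Hochberg method".

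Comparisons are planned both within and between the arms. Section 3.1 gives the status of the work: "as an exploratory goal, we will perform genome-wide expression analysis". Section 8.1 sets the number of men at 11 per arm, 22 in total.

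Neither section mentions correlation between genes, permutation of patient labels, or a set test that adjusts for correlation. Neither states which Wilcoxon test is meant, what is ranked, the null distribution, the false discovery rate, or the number and size of the sets.

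**The concern.** The steps run from one statistic per gene, to gene sets, to a Wilcoxon test. The natural reading is a rank-sum test of the genes in a set against the genes outside it. The null distribution of that test takes genes as the independent units. The independent units here are the men. Genes in one pathway tend to rise and fall together across the same specimens, so their statistics are correlated even when the drug does nothing, and the rank sum of a set varies more than the test assumes.

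No other step repairs this. The mixed model and the empirical Bayes moderation act within a gene. Benjamini-Hochberg takes the set-level P values as given, and if those are too small its error control is lost.

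At stake is the trial's only exploratory objective. A pathway list from this analysis could contain false entries with no drug effect present, and the reader would believe that a false discovery procedure had been applied to it.

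**Working it through.** **The plan's own figure.** Section 8.3 gives no figure for the enrichment analysis. The only computed figure in section 8 is the primary-endpoint sample size of 11 per arm. It reproduces exactly with 10% v 70%, two-sided alpha 0.10, 80% power and a continuity correction. It has no bearing on this point except to fix the number of men.

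**Inputs.** From the documents: 11 men per arm (8.1), gene-by-gene modelling, Wilcoxon enrichment and Benjamini-Hochberg (6.2.4, 8.3). Assumed, because the documents do not give them: set size m from 20 to 200, average within-set correlation rho from 0.01 to 0.20, 500 sets (200 in a separate simulation), and a false discovery rate of 5%.

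**Formula.** Take genes outside the set as uncorrelated with the set and with one another. The variance of the set's rank-sum statistic is then multiplied by about

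VIF = 1 + (m - 1) × rho,

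and a nominal two-sided 5% test has true size

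2 × [1 - Phi(1.96 / sqrt(VIF))].

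**One case in full.** With m=100 and rho=0.05, VIF = 1 + 99 × 0.05 = 5.95. Its square root is 2.439, and 1.96/2.439 = 0.804. The true size is 2 × [1 - Phi(0.804)] = 42%.

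**Range.** The last column is the mean number of sets passing Benjamini-Hochberg at 5% out of 500 null sets. It was found by drawing 500 independent normal statistics, all with the VIF shown.

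| m | rho | VIF | True size at nominal 5% | False sets of 500 |
|---|---|---|---|---|
| any | 0 | 1.00 | 5% | 0.06 |
| 20 | 0.01 | 1.19 | 7% | 0.2 |
| 50 | 0.01 | 1.49 | 11% | 1.4 |
| 50 | 0.02 | 1.98 | 16% | 11 |
| 100 | 0.01 | 1.99 | 16% | 11 |
| 50 | 0.05 | 3.45 | 29% | 75 |
| 100 | 0.05 | 5.95 | 42% | 162 |
| 200 | 0.10 | 20.90 | 67% | 320 |

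**Check by simulating expression data.** Setting: 11 v 11 men, one value per gene per man, no drug effect, 200 disjoint equicorrelated sets, a moderated t statistic per gene, a rank-sum test of in-set against out-of-set genes, Benjamini-Hochberg at 5%, and 60 replicates per case.

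- Independent genes, m=100: size 5.0%, 0.08 false sets of 200. The test is valid when its assumption holds.
- m=20, rho=0.01: size 7.0%, 0.03 false sets.
- m=50, rho=0.05: size 28.6%, 29 false sets.
- m=100, rho=0.05: size 41.9%, 65 false sets. That is 65/200 = 32%, the same share as 162/500.

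**The same test with its variance adjusted** for correlation estimated from the residuals: size 3% to 5% and on average 0.00 to 0.08 false sets of 200, in every case tried (m = 20, 50, 100; rho = 0 to 0.20).

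**The case against.** **The test is inferred.** The documents do not say that genes are ranked. A Wilcoxon test on one pathway score per man, or one referred to permuted patient labels, would not have this defect. This stands as a limit on certainty. But the plan mentions neither alternative, and its order (per-gene statistics, then sets, then Wilcoxon) points to gene ranks. If another test was intended, the text still has to say so.

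**The size depends on inputs that the plan does not give.** This also stands. A reader might infer that the P values are bound to be far too small and that many false pathways will certainly pass. The documents do not support that: with sets of 20 genes and rho=0.01 the inflation is negligible. It becomes material at about rho=0.05 at every set size tried, and at lower correlation when sets are large.

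**The calculation is simplified.** The formula ignores correlation among genes outside the set, and the counts of 500 treat the sets as independent and equally inflated. Real annotation sets overlap and differ in size. The counts would change, but not the direction.

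**The consequence is limited.** The analysis is labelled exploratory, and section 3.1 promises confirmation of selected genes. That is a partial safeguard, because it works on genes and not on sets. A reader might also infer from section 1.5 that pathway lists will be used to choose patients or combinations. That section says only, and tentatively, that knowing the molecular responses might help with selection and timing. It does not name the pathway lists.

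**Conclusion.** The point holds conditionally. As written, the plan applies a Wilcoxon enrichment test with no allowance for correlation between genes measured on the same 22 men. On its ordinary reading the set-level P values are too small, and the planned Benjamini-Hochberg step does not deliver the control that it implies. How far it falls short rests on assumed correlation, set size, number of sets and false discovery rate: from almost nothing for small, weakly correlated sets to roughly a third of null sets passing at m=100 and rho=0.05. The defect is confined to the exploratory objective. The primary Gli1 endpoint, the sample size and the secondary endpoints do not depend on it. It should be corrected because the plan names a false discovery procedure and the remedy is cheap, but it does not threaten the trial's main conclusion.

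**What to change.** In sections 6.2.4 and 8.3:

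1. Replace the Wilcoxon enrichment test with one competitive set test that allows for inter-gene correlation: CAMERA with the correlation estimated from the data, or its correlation-adjusted rank version, which stays closest to the present plan.
2. Run it from the same linear-model fit in R/Bioconductor, on the arm-by-specimen contrast (difference between arms in the biopsy-to-prostatectomy change) and on the within-arm contrasts that the plan also intends.
3. State the ranked or tested statistic and the null hypothesis. Then apply Benjamini-Hochberg across sets at a stated false discovery rate.

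Choose one test and name it. ROAST tests a self-contained null, which is a different question from enrichment relative to other genes. Permuting arm labels by man suits the between-arm contrast but not the within-arm comparisons. They are not interchangeable with CAMERA.

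The cost is a short change of wording and a little more analysis work. No patient, specimen or visit changes. The downside is that fewer sets will be declared significant.

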## **9 Ethical Considerations**

### **9.1 Ethics and good clinical practice**

This study must be carried out in compliance with the protocol and GCP, as described in:

1. ICH Harmonized Tripartite Guidelines for Good Clinical Practice 1996.
2. US 21 Code of Federal Regulations dealing with clinical studies (including parts 50 and 56 concerning informed consent and IRB regulations).
3. Declaration of Helsinki, concerning medical research in humans (Recommendations Guiding Physicians in Biomedical Research Involving Human Subjects, Helsinki 1964, amended Tokyo 1975, Venice 1983, Hong Kong 1989, Somerset West 1996).

The investigator agrees to adhere to the instructions and procedures described in it and thereby to adhere to the principles of Good Clinical Practice that it conforms to.

### **9.2 Institutional review board / Independent ethics committee**

Before implementing this study, the protocol, the proposed informed consent form and other information to subjects, must be reviewed by a properly constituted Institutional Review Board/Independent Ethics Committee (IRB/IEC/REB). A signed and dated statement that the protocol and informed consent have been approved by the IRB/IEC/REB must be given to Novartis before study initiation. The name and occupation of the chairman and the members of the IRB/IEC/REB must be supplied to Novartis. Any amendments to the protocol, other than administrative ones, must be approved by this committee.

### **9.3 Informed consent**

The investigator must explain to each subject (or legally authorized representative) the nature of the study, its purpose, the procedures involved, the expected duration, the potential risks and benefits involved and any discomfort it may entail. Each subject must be informed that participation in the study is voluntary and that he may withdraw from the study at any time

Protocol Version 3: October 6, 2015

and that withdrawal of consent will not affect his subsequent medical treatment or relationship with the treating physician.

This informed consent should be given by means of a standard written statement, written in non-technical language. The subject should read and consider the statement before signing and dating it, and should be given a copy of the signed document. If the subject cannot read or sign the documents, oral presentation may be made or signature given by the subject's legally appointed representative, if witnessed by a person not involved in the study, mentioning that the patient could not read or sign the documents. No patient can enter the study before his informed consent has been obtained. The informed consent form is considered to be part of the protocol, and must be submitted by the investigator with it for IRB/IEC/REB approval.

Fertile men should be informed that taking the study medication may involve unknown risks to a conceived fetus if pregnancy were to occur during the study and agree that in order to participate in the study they must adhere to the contraception requirement for the duration of the study. If there is any question that the patient will not reliably comply, they should not be entered in the study.

## **9.4 Discontinuation of the study**

Novartis reserves the right to discontinue support for any study under the conditions specified in the clinical trial agreement.

## **9.5 Amendments to the protocol**

Any change or addition to this protocol requires a written protocol amendment that must be approved by Novartis and the investigator before implementation. Amendments significantly affecting the safety of subjects, the scope of the investigation or the scientific quality of the study, require additional approval by the IRB/IEC/REB. A copy of the written approval of the IRB/IEC/REB, must be sent to Novartis.

Amendments affecting only administrative aspects of the study do not require formal protocol amendments or IRB/IEC/REB approval but the IRB/IEC/REB of each center must be kept informed of such administrative changes.

### **9.5.1 Publication of results**

Any formal presentation or publication of data from this trial may be published after review and comment by Novartis and prior to any outside submission. Novartis must receive copies of any intended communication in advance of publication (at least twenty-one working days for presentational materials and abstracts and thirty working days for manuscripts). These requirements acknowledge Novartis' responsibility to provide peer input regarding the scientific content and conclusions of such publications or presentations. Principal Investigator/Institution shall have the final authority to determine the scope and content of its publications, provided such authority shall be exercised with reasonable regard for the interests of Novartis and, in accord with the trial contract and shall not permit disclosure of Novartis confidential or proprietary information.

### **9.5.2 Disclosure and confidentiality**

The investigator agrees to keep all information provided by Novartis in strict confidence and to request similar confidentiality from his/her staff and the IRB/IEC/REB. Study documents provided by Novartis (investigators'

Protocol Version 3: October 6, 2015

brochures and other material) will be stored appropriately to ensure their confidentiality. The information provided by Novartis to the investigator may not be disclosed to others without direct written authorization from Novartis, except to the extent necessary to obtain informed consent from patients who wish to participate in the trial.

### **9.5.3 Declaration of Helsinki**

The investigator must conduct the trial in accordance with the principles of the Declaration of Helsinki. Copies of the Declaration of Helsinki and amendments will be provided upon request or can be accessed via the website of the World Medical Association at [http://www.wma.net/e/policy/17-c\\_e.html](http://www.wma.net/e/policy/17-c_e.html).

